8.3.1 Solicited AEs (Reactogenicity)

Solicited AEs can be divided into immediate post-vaccination events, local reactogenicity events, and systemic reactogenicity events. The immediate events will be recorded by the study staff in the 20 minutes after each vaccination. All solicited events with corresponding grades as described in [Section 8.4.3](#) will be evaluated. These severity grades include mild, moderate, or severe.

Local and systemic reactogenicity events will then be recorded by the parent/guardian daily from Day 1 to Day 8 after the first vaccine or placebo and the 7 days following the second vaccination for participants in Cohorts 4, 5, 6, and 7 with the use of a memory aid. The local events are those

in and around the nares, where the vaccine is administered. Local and systemic events are described in [Table 4](#), below.

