5.5. Missing Data and Outliers

No imputation is planned for missing data.

Any data point that appears to be erroneous or inexplicable based on the observed data distribution and the statistical team's understanding of the analysis variables will be investigated as a possible outlier. If data points are identified as outliers, sensitivity analyses may be performed to examine the impact of including or excluding the outliers. Any substantive differences in these analyses will be reported.

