8.1.1.2. Solicited Events/Symptoms

Participant-level summaries of solicited AE data will be generated for solicited events applicable to each participant based on their age at enrollment. For summaries by severity, the maximum severity over 7 days post applicable vaccinations will be identified for each participant. For summaries independent of severity, a participant will be classified as reporting the event if their maximum severity for the event was classified as mild or worse. Denominators for percentages will be the number of participants with solicited data available for the given solicited event in the specified group for which the solicited event is applicable. All placebo participants ages 2-8 years old will be summarized together, except for events post dose 2, and solicited events of vaccine recipients post first study vaccination in Cohorts 3 and 4 will be summarized together.

The number and percentage of participants reporting any solicited event, any local event, any systemic event, and each applicable solicited adverse event individually will be summarized by maximum severity and vaccination group, separately for each vaccination and after any vaccination ([Table 26](#) through [Table 28](#)) and presented graphically in a bar chart ([Figure 14](#) through [Figure 23](#)).

The number of participants reporting a solicited adverse event will be summarized by day post vaccination for each vaccination and after any vaccination ([Table 29](#) through [Table 39](#)) and presented graphically in a bar chart ([Figure 24](#) through [Figure 33](#)).

All reported solicited events will be presented in participant listings separately for local events ([Listing 11](#)) and systemic events ([Listing 12](#)).

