	Mild	x/x	x	x/x	x	x/x	x	x/x	x	x/x	x	x/x	x
	Moderate	x/x	x	x/x	x	x/x	x	x/x	x	x/x	x	x/x	x
	Severe	x/x	x	x/x	x	x/x	x	x/x	x	x/x	x	x/x	x
Vomiting	None	x/x	x	x/x	x	x/x	x	x/x	x	x/x	x	x/x	x
	Mild	x/x	x	x/x	x	x/x	x	x/x	x	x/x	x	x/x	x
	Moderate	x/x	x	x/x	x	x/x	x	x/x	x	x/x	x	x/x	x
	Severe	x/x	x	x/x	x	x/x	x	x/x	x	x/x	x	x/x	x
Diarrhea	None	x/x	x	x/x	x	x/x	x	x/x	x	x/x	x	x/x	x
	Mild	x/x	x	x/x	x	x/x	x	x/x	x	x/x	x	x/x	x
	Moderate	x/x	x	x/x	x	x/x	x	x/x	x	x/x	x	x/x	x
	Severe	x/x	x	x/x	x	x/x	x	x/x	x	x/x	x	x/x	x
Eye Pruritus	None	x/x	x	x/x	x	x/x	x	x/x	x	x/x	x	x/x	x
	Mild	x/x	x	x/x	x	x/x	x	x/x	x	x/x	x	x/x	x
	Moderate	x/x	x	x/x	x	x/x	x	x/x	x	x/x	x	x/x	x

Table 26: Summary of Post-Dosing Solicited Adverse Events Through 7 Days Post Dose 1 by Cohort and Vaccination Group - Safety Population (continued)

Symptom	Severity	9-17 yrs, 10 ⁹ TCID ₅₀ Sing2016 M2SR or Placebo, 1 Dose (N=X)				2-8 yrs, 10 ⁸ TCID ₅₀ Sing2016 M2SR, 1 Dose (N=X)	2-8 yrs, 10 ⁹ TCID ₅₀ Sing2016 M2SR, 1 or 2 Doses (N=X)	2-8 yrs, Placebo, 1 or 2 Doses (N=X)	All Participants (N=X)				
		Vaccine (N=X)		Placebo (N=X)					Vaccine (N=X)		Placebo (N=X)		
		n/N*	%	n/N*	%	n/N*	%	n/N*	%	n/N*	%	n/N*	%
	Severe	x/x	x	x/x	x	x/x	x	x/x	x	x/x	x	x/x	x
Eye Redness	None	x/x	x	x/x	x	x/x	x	x/x	x	x/x	x	x/x	x
	Mild	x/x	x	x/x	x	x/x	x	x/x	x	x/x	x	x/x	x
	Moderate	x/x	x	x/x	x	x/x	x	x/x	x	x/x	x	x/x	x
	Severe	x/x	x	x/x	x	x/x	x	x/x	x	x/x	x	x/x	x
Allergic Skin Reaction	None	x/x	x	x/x	x	x/x	x	x/x	x	x/x	x	x/x	x
	Mild	x/x	x	x/x	x	x/x	x	x/x	x	x/x	x	x/x	x
	Moderate	x/x	x	x/x	x	x/x	x	x/x	x	x/x	x	x/x	x
	Severe	x/x	x	x/x	x	x/x	x	x/x	x	x/x	x	x/x	x
Fever	None	x/x	x	x/x	x	x/x	x	x/x	x	x/x	x	x/x	x
	Mild	x/x	x	x/x	x	x/x	x	x/x	x	x/x	x	x/x	x
	Moderate	x/x	x	x/x	x	x/x	x	x/x	x	x/x	x	x/x	x
	Severe	x/x	x	x/x	x	x/x	x	x/x	x	x/x	x	x/x	x

N = Number of participants in the safety population who received dose 1.

N* = Number of participants in the safety population with any solicited event data recorded post dose 1 and belonging to the respective age range for the specified event.

n = Number of participants in the safety population reporting the specified event type.

Participants are counted once at the highest severity reported post dose 1.

Events are reported for 7 days post dose 1.

Event applies to all age ranges, unless otherwise noted by ^a, ^b, or ^c.^a Applicable for participants 9-17 years old.^b Applicable for participants 4-8 years old.^c Applicable for participants 2-3 years old.

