Table 27: Summary of Post-Dosing Solicited Adverse Events Through 7 Days Post Dose 2 by Cohort and Vaccination Group – Safety Population (continued)

Symptom	Severity	2-8 yrs, 10 ⁹ TCID ₅₀ Sing2016 M2SR or Placebo, 2 Doses (N=X)			
		Vaccine (N=X)		Placebo (N=X)	
		n/N*	%	n/N*	%
Myalgia ^a	Severe	x/x	x	x/x	x
	None	x/x	x	x/x	x
	Mild	x/x	x	x/x	x
	Moderate	x/x	x	x/x	x
Arthralgia ^a	Severe	x/x	x	x/x	x
	None	x/x	x	x/x	x
	Mild	x/x	x	x/x	x
	Moderate	x/x	x	x/x	x
Headache ^a	Severe	x/x	x	x/x	x
	None	x/x	x	x/x	x
	Mild	x/x	x	x/x	x
	Moderate	x/x	x	x/x	x
Irritability / Fussiness ^b	Severe	x/x	x	x/x	x
	None	x/x	x	x/x	x
	Mild	x/x	x	x/x	x
	Moderate	x/x	x	x/x	x
Decreased Activity	Severe	x/x	x	x/x	x
	None	x/x	x	x/x	x
	Mild	x/x	x	x/x	x
	Moderate	x/x	x	x/x	x
Decreased Appetite	Severe	x/x	x	x/x	x
	None	x/x	x	x/x	x
	Mild	x/x	x	x/x	x
	Moderate	x/x	x	x/x	x

Table 27: Summary of Post-Dosing Solicited Adverse Events Through 7 Days Post Dose 2 by Cohort and Vaccination Group – Safety Population (continued)

Symptom	Severity	2-8 yrs, 10 ⁹ TCID ₅₀ Sing2016 M2SR or Placebo, 2 Doses (N=X)			
		Vaccine (N=X)		Placebo (N=X)	
		n/N*	%	n/N*	%
	Mild	x/x	x	x/x	x
	Moderate	x/x	x	x/x	x
	Severe	x/x	x	x/x	x
Abdominal Pain ^a	None	x/x	x	x/x	x
	Mild	x/x	x	x/x	x
	Moderate	x/x	x	x/x	x
	Severe	x/x	x	x/x	x
Nausea ^a	None	x/x	x	x/x	x
	Mild	x/x	x	x/x	x
	Moderate	x/x	x	x/x	x
	Severe	x/x	x	x/x	x
Vomiting	None	x/x	x	x/x	x
	Mild	x/x	x	x/x	x
	Moderate	x/x	x	x/x	x
	Severe	x/x	x	x/x	x
Diarrhea	None	x/x	x	x/x	x
	Mild	x/x	x	x/x	x
	Moderate	x/x	x	x/x	x
	Severe	x/x	x	x/x	x
Eye Pruritus	None	x/x	x	x/x	x
	Mild	x/x	x	x/x	x
	Moderate	x/x	x	x/x	x

Table 27: Summary of Post-Dosing Solicited Adverse Events Through 7 Days Post Dose 2 by Cohort and Vaccination Group – Safety Population (continued)

Symptom	Severity	2-8 yrs, 10 ⁹ TCID ₅₀ Sing2016 M2SR or Placebo, 2 Doses (N=X)			
		Vaccine (N=X)		Placebo (N=X)	
		n/N*	%	n/N*	%
Eye Redness	Severe	x/x	x	x/x	x
	None	x/x	x	x/x	x
	Mild	x/x	x	x/x	x
	Moderate	x/x	x	x/x	x
Allergic Skin Reaction	Severe	x/x	x	x/x	x
	None	x/x	x	x/x	x
	Mild	x/x	x	x/x	x
	Moderate	x/x	x	x/x	x
Fever	Severe	x/x	x	x/x	x
	None	x/x	x	x/x	x
	Mild	x/x	x	x/x	x
	Moderate	x/x	x	x/x	x
	Severe	x/x	x	x/x	x

N = Number of participants in the safety population who received dose 2.
N* = Number of participants in the safety population with any solicited event data recorded post dose 2 and belonging to the respective age range for the specified event.

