	None																		
	Mild																		
	Moderate																		
Eye Pruritus	Severe																		
	None																		
	Mild																		

Table 29: Participant-Level Solicited Event Rate by Symptom, Severity, and Day Post Dosing – Participants 9-17 Years Old, 10⁹ TCID₅₀ Sing2016 M2SR, 1 Dose - Safety Population (N=X) (continued)

Symptom	Severity	Post-Dose		Day 1		Day 2		Day 3		Day 4		Day 5		Day 6		Day 7		Day 8+	
		n/N*	%	n/N*	%	n/N*	%	n/N*	%	n/N*	%	n/N*	%	n/N*	%	n/N*	%	n/N*	%
	Moderate																		
	Severe																		
Eye Redness	None																		
	Mild																		
	Moderate																		
	Severe																		
Allergic Skin Reaction	None																		
	Mild																		
	Moderate																		
	Severe																		
Fever	None																		
	Mild																		
	Moderate																		
	Severe																		

N = Number of participants in the safety population

N* = Number of participants in the safety population with any solicited event data recorded post dosing.

n = Number of participants in the safety population reporting the specified event type.

Participants are counted once at the highest severity reported at each day.

Similar Tables:**Table 30: Participant-Level Solicited Event Rate by Symptom, Severity, and Day Post Dosing – Participants 9-17 Years Old, Placebo, 1 Dose - Safety Population (N=X)**

Implementation Note: This table will be similar to Table 29.

Table 31: Participant-Level Solicited Event Rate by Symptom, Severity, and Day Post Dose 1 – Participants 2-8 Years Old, 10⁸ TCID₅₀ Sing2016 M2SR, 1 Dose - Safety Population (N=X)

Symptom	Severity	Post-Dose		Day 1		Day 2		Day 3		Day 4		Day 5		Day 6		Day 7		Day 8+	
		n/N*	%	n/N*	%	n/N*	%	n/N*	%	n/N*	%	n/N*	%	n/N*	%	n/N*	%	n/N*	%
Any Solicited Event	None	x/x	x	x/x	x	x/x	x	x/x	x	x/x	x	x/x	x	x/x	x	x/x	x	x/x	x
	Mild																		
	Moderate																		
	Severe																		
Local Solicited Events																			
Any Local Solicited Event	None																		
	Mild																		
	Moderate																		
	Severe																		
Rhinorrhea	None																		
	Mild																		
	Moderate																		
	Severe																		
Stuffy Nose / Congestion	None																		
	Mild																		
	Moderate																		
	Severe																		
Sneezing	None																		
	Mild																		
	Moderate																		
	Severe																		

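### The 7-day solicited-event tables count a child with a clean 20-minute check and no diary as event-free, so any missing diary lowers the primary reactogenicity rates

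*SAP*

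**What the plan says.** Primary endpoints 1 and 2 (SAP 3.2) are the number and percentage of children with solicited local and systemic events in the 7 days after each dose.

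The data come from two sources. Protocol 8.3.1 says of the clinic observation: "The immediate events will be recorded by the study staff in the 20 minutes after each vaccination". Its next sentence says that all solicited events, with their grades, will be evaluated. Parents then record local and systemic events daily on a memory aid from Day 1 to Day 8, and for 7 days after a second dose. SAP 8.1 counts both sources as solicited reporting, and the by-day table shells carry a Post-Dose column ahead of Day 1.

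The denominator is described in several places:

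- Tables 26, 31 and 38 (footnotes): "Number of participants in the safety population with any solicited event data recorded post dose 1", within the age range for the event.
- Table 27 (footnote): "Number of participants in the safety population with any solicited event data recorded post dose 2", with the same age condition. Table 28 is to follow Table 27 with its footnotes updated.
- Table 29 (footnote, by day): "Number of participants in the safety population with any solicited event data recorded post dosing".
- SAP 8.1.1.2 (body text): "Denominators for percentages will be the number of participants with solicited data available for the given solicited event in the specified group".
- SAP 8 and 5.1 (general rules): percentages rest on non-missing observations, or in SAP 8 on the Safety population, unless otherwise specified.

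On classification, the Table 26 footnote says: "Participants are counted once at the highest severity reported post dose 1". SAP 8.1.1.2 adds that, in summaries that ignore severity, "a participant will be classified as reporting the event if their maximum severity for the event was classified as mild or worse". The tables carry a None row for everyone else in N*. On missing data, SAP 5.5 says: "No imputation is planned for missing data".

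**The concern.** A 7-day event rate needs children who were observed for some of the 7 days. Under the footnotes, one record from the first 20 minutes is enough to enter N*. A child whose check was clean and whose family returned no diary then has a recorded maximum severity of none, and is reported as free of fever, cough or rhinorrhea for a week in which nobody recorded anything.

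Against the true 7-day rate this error can only run downward, because an unobserved child can lose events but cannot gain them. In a paediatric trial whose primary objective is safety, that is the favourable direction for the product. The comparison between vaccine and placebo would also be affected if diary return differed between groups.

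The body text and the footnotes are also not the same rule, so two programmers could produce different denominators for a primary endpoint.

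**Working it through.** **Does a child with no diary enter N*?** The 20-minute check follows every vaccination (Protocol 8.3.1), and the SAP treats it as solicited data (SAP 8.1). The footnote asks for any solicited data after the dose, so the check alone satisfies it. SAP 8.1.1.2 is narrower because the data must concern the given event. If all solicited events are graded at 20 minutes, as Protocol 8.3.1 indicates, the check satisfies that rule too. Neither text asks for a diary day.

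**The plan's own figures.** SAP Table 4 gives exact Clopper-Pearson limits that depend on the denominator. They reproduce: 12/30 = 40.0% (22.7, 59.4); 0/30 has an upper limit of 1 - 0.025^(1/30) = 11.6%; 4/15 = 26.7% (7.8, 55.1); 4/10 = 40.0% (12.2, 73.8).

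**Effect of the rule.** Let N be the children in N* under the footnote, m those with no diary, x those with the event, and k the no-diary children whose event was seen at 20 minutes.

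- Footnote rate: x/N.
- Rate requiring a diary but keeping immediate events: x/(N - m + k).
- Ratio of the first to the second: (N - m + k)/N. It is lowest, at (N-m)/N, when k = 0.

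The value of m is an assumption, because the documents give no diary-return rate. Group sizes come from SAP Tables 2 and 4: 30 for the vaccine group in Cohort 1 or 2, or for the Cohort 3 and 4 vaccine groups pooled after dose 1; 15 vaccine and 10 placebo in Cohort 4 after dose 2. Event counts are illustrative. With k = 0:

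| N | x | m | Footnote rule | Diary required |
|---|---|---|---|---|
| 30 | 12 | 1 | 40.0% (22.7, 59.4) | 12/29 = 41.4% (23.5, 61.1) |
| 30 | 12 | 3 | 40.0% (22.7, 59.4) | 12/27 = 44.4% (25.5, 64.7) |
| 30 | 12 | 5 | 40.0% (22.7, 59.4) | 12/25 = 48.0% (27.8, 68.7) |
| 30 | 0 | 3 | 0% (0, 11.6) | 0/27 = 0% (0, 12.8) |
| 15 | 4 | 1 | 26.7% (7.8, 55.1) | 4/14 = 28.6% (8.4, 58.1) |
| 15 | 4 | 3 | 26.7% (7.8, 55.1) | 4/12 = 33.3% (9.9, 65.1) |
| 10 | 4 | 1 | 40.0% (12.2, 73.8) | 4/9 = 44.4% (13.7, 78.8) |
| 10 | 4 | 2 | 40.0% (12.2, 73.8) | 4/8 = 50.0% (15.7, 84.3) |

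For N = 30 the factor (N-m)/N is 29/30 = 0.967, 27/30 = 0.900 and 25/30 = 0.833 at m = 1, 3 and 5. If one of three no-diary children had the event at 20 minutes (k = 1), 12/30 compares with 12/28 = 42.9%, so the gap is smaller. At m = 0 the two rules agree.

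**By-day tables.** The Table 29 footnote ties N* to data recorded after dosing, not to the day in the column. Read literally, a child with no Day 5 entry is still in the Day 5 denominator. However, each day column in the shells prints its own n/N*, which would also fit a day-specific count. The text does not settle which is meant.

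**The case against.** The strongest reply is that the footnotes are shell text. The body of the SAP bases percentages on data available for the event (8.1.1.2) and on non-missing observations (8 and 5.1), and the repeated n/N* by day suggests day-specific counts. This stands as far as it goes. The by-day problem is one reading of an ambiguous footnote, and a reader should not infer that any planned by-day decline would be an artefact. For Tables 26-28 the reply narrows the problem without removing it, since no version requires a diary day.

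A second reply is that the documents do not show that a negative grade for every symptom is stored at 20 minutes. Protocol 8.3.1 lists immediate events as a separate class, and the sentence about evaluating all solicited events does not say how they are recorded. This is fair. If only some symptoms are graded then, the 8.1.1.2 rule would exclude no-diary children for the others, but the footnote would still admit them.

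Third, missing diaries may be few. Phone contacts are scheduled on Days 3 and 8 and again after dose 2, and disposition Table 8 reports completion of 7-day follow-up. Both may limit or reveal missing data. Neither enters the definition of N*.

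A reader might also infer that the footnote breaches SAP 5.5. That goes too far: it is an inclusion rule applied to recorded values, and it has the effect of imputing no event without being stated as imputation.

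**Conclusion.** The concern holds conditionally. As written, the N* footnotes for Tables 26-28 let a clean 20-minute check stand in for 7 days of observation. Whenever a diary is missing, the reported primary reactogenicity rate is too low, by up to the factor (N-m)/N: 40.0% instead of 44.4% for 12 events with 3 of 30 diaries missing, and 26.7% instead of 33.3% for 4 events with 3 of 15 missing. Zero-event upper limits are also too low (11.6% instead of 12.8% for 3 of 30).

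The size rests on an assumed m and, for the diary-based rate to represent the whole group, on children without diaries resembling those with them. It also rests on the 20-minute check supplying a record. A reader might infer that the rates are biased downward in both arms as a matter of fact. The documents do not support that: they report no missing diaries, and with complete diaries the effect is nil.

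The conflict between the footnotes and SAP 8.1.1.2, and the undefined by-day N*, need resolving whatever m turns out to be.

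**What to change.** 1. In Tables 26-28 and Figures 14-23, define N* for each event as children with at least one diary record for that event, made after the clinic observation for that dose, plus any child with that event recorded at the 20-minute check. Immediate events belong to the 7-day endpoint and must stay in its numerator, so they should not be moved out to a Post-Dose column alone.
2. In Tables 29-39 and Figures 24-33, define N* for each column as children with a record for that day. The Post-Dose column uses children observed at 20 minutes.
3. Bring SAP 8.1.1.2 and the footnotes to one wording.
4. Report, by group and dose, the number of dosed children with no diary and with an incomplete diary. A child with only a Day 1 entry still counts as event-free under item 1, so this row is needed to judge the rates.

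The cost is a change to footnotes and programming, with no change to data collection or conduct. Denominators become slightly smaller and rates slightly less favourable. Because a child without a diary enters N* only after an immediate event, item 1 leans slightly toward a higher rate, and the counts in item 4 show how much this could matter.

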14.3.2 Listings of Deaths, Other Serious and Significant Adverse Events

Table 110: Adverse Events of Special Interest

Part 1:											
Analysis Group	Participant ID	AE Number	Adverse Event	Associated with Dose No.	No. of Days Post Associated Dose	Duration (Days)	MedDRA System Organ Class	MedDRA Preferred Term	Severity	SAE?	
Part 2:											
Analysis Group	Participant ID	AE Number	Adverse Event	Action Taken with Study Vaccination	Participant Discontinued Due to AE?	Relationship to Study Vaccination	If Not Related, Alternative Etiology	NOCMC?	Unanticipated Problem?	Outcome	Comments

Similar Tables:

Table 111: Serious Adverse Events

Implementation Note: This will be similar to Table 110. This table will exclude the “SAE?” column, will have “Relationship to Study Vaccination” and “If Not Related, Alternative Etiology” as the last columns in Part 1, and will include an “AESI?” column to the left of the “NOCMC?” column.

Table 112: New-Onset Chronic Medical Conditions

Implementation Note: This will be similar to Table 110. This table will replace the “NOCMC?” column with “AESI?”.

Table 113: Listing of Wheezing Events and Corresponding Vital Signs and Respiratory Virus Panels**Part 1**

Analysis Group	Participant ID	AE Number	Adverse Event	Study Day Event Started	Associated with Dose No.	No. of Days Post Associated Dose	Duration (Days)	# of Days Post Dose until Episode met Case Definition of Acute Wheeze	Severity	Relationship to Study Treatment	If Not Related, Alternate Etiology

Part 2

Analysis Group	Participant ID	AE Number	Adverse Event	Study Day Event Started	Participant Discontinued Due to AE?	Unanticipated Problem?	Outcome	MedDRA System Organ Class	MedDRA Preferred Term	Comments

Part 3

Analysis Group	Participant ID	AE Number	Adverse Event	Study Day Event Started	Study Day of Vital Signs	Temperature (°F)	Systolic Blood Pressure (mmHg)	Diastolic Blood Pressure (mmHg)	Respiratory Rate (breaths/min)	Oxygen Saturation (%)	Inspiratory: Expiratory (Ratio)

Part 4

Analysis Group	Participant ID	AE Number	Adverse Event	Study Day Event Started	Study Day of Virus Panel	Result of Qualitative RT-PCR Multiplex Respiratory Virus Assay	Positive or Equivocal Viruses from Qualitative RT-PCR Multiplex Respiratory Virus Assay	Name of Other Infectious Disease Diagnostic Test Performed	Results from Other Infectious Disease Diagnostic Test

14.4 Summary of Concomitant Medications

Table 114: Number and Percent of Participants Reporting Pre-Existing and Concomitant Medications by WHO Drug Classification, Cohort, and Vaccination Group - Safety Population

[Implementation Note: WHO Drug Code Level Codes will be sorted by frequency across all participants, most to least common.]

WHO Drug Code Level 1, Anatomic Group	WHO Drug Code Level 2, Therapeutic Subgroup	9-17 yrs, 10 ⁹ TCID ₅₀ Sing2016 M2SR or Placebo, 1 Dose (N=X)				2-8 yrs, 10 ⁸ TCID ₅₀ Sing2016 M2SR or Placebo, 1 Dose (N=X)				2-8 yrs, 10 ⁹ TCID ₅₀ Sing2016 M2SR or Placebo, 1 Dose (N=X)				2-8 yrs, 10 ⁹ TCID ₅₀ Sing2016 M2SR or Placebo, 2 Doses (N=X)				All Participants ^a (N=X)	
		Vaccine (N=X)		Placebo (N=X)		Vaccine (N=X)		Placebo (N=X)		Vaccine (N=X)		Placebo (N=X)		Vaccine (N=X)		Placebo (N=X)			
		n	%	n	%	n	%	n	%	n	%	n	%	n	%	n	%		
Any Level 1 Codes	Any Level 2 Codes	x	x	x	x	x	x	x	x	x	x	x	x	x	x	x	x		
[ATC Level 1 – 1]	Any [ATC 1 – 1]	x	x	x	x	x	x	x	x	x	x	x	x	x	x	x	x		
	[ATC 2 – 1]	x	x	x	x	x	x	x	x	x	x	x	x	x	x	x	x		
	[ATC 2 – 2]																		
	[ATC 2 – 3]																		
[ATC Level 1 – 2]	Any [ATC 1 – 2]	x	x	x	x	x	x	x	x	x	x	x	x	x	x	x	x		
	[ATC 2 – 1]																		
	[ATC 2 – 2]																		
	[ATC 2 – 3]																		

N = Number of participants in the safety population; n = Number of participants in the safety population reporting taking at least one medication in the specific WHO Drug Class.

9.1 Overall Study Design and Plan Description

Figure 1: Study Schema

10.1 Disposition of Participants

[figure not shown]
Figure 2: CONSORT Flow Diagram

14.2.1 Immunogenicity Response Figures

Figure 3: Geometric Mean Hemagglutination Inhibition (HAI) Antibody Titers in Serum Against A/Singapore/INFIMH-16-0019/2016 and Associated 95% Confidence Intervals by Cohort and Vaccination Group – Modified Intent-to-Treat Population

[Implementation note: The figure below is for reference only. This figure will display the geometric mean response with 95% CIs at each visit and individual participant trajectories at a decreased transparency. Immunogenicity results will be presented in three panels (9-17 year olds, 2-8 year olds, all participants) and different colors/markers to distinguish analysis groups. Groups include: 9-17 yrs, 10^9 TCID₅₀ Sing2016 M2SR, 1 Dose; 9-17 yrs, Placebo, 1 Dose; 2-8 yrs, 10^8 TCID₅₀ Sing2016 M2SR, 1 Dose; 2-8 yrs, 10^9 TCID₅₀ Sing2016 M2SR, 1 Dose; 2-8 yrs, 10^9 TCID₅₀ Sing2016 M2SR, 2 Doses; 2-8 yrs, Placebo, 1 Dose; 2-8 yrs, Placebo, 2 Doses; All Vaccine Recipients; All Placebo Participants]

Similar Figures:

Figure 4: Geometric Mean Influenza Microneutralization (MN) Antibody Titers in Serum against A/Singapore/INFIMH-16-0019/2016 and Associated 95% Confidence Intervals by Cohort and Vaccination Group – Modified Intent-to-Treat Population

Implementation Note: This will be similar to Figure 3.

Figure 5: Mean ECL Signal for sIgA as measured by the Binding Antibody Multiplex Assay and Associated 95% Confidence Intervals by Antigen, Cohort, and Vaccination Group – Modified Intent-to-Treat Population

Implementation Note: This will be similar to Figure 3. Antigens will be presented as panels. The figure will be split into different parts (e.g., Parts a, b, c, etc.) if all antigens are unable to be presented in a readable manner within one figure.

Figure 6: Mean Total IgA Concentration for sIgA as measured by the Binding Antibody Multiplex Assay and Associated 95% Confidence Intervals by Antigen, Cohort, and Vaccination Group – Modified Intent-to-Treat Population

Implementation Note: This will be similar to Figure 3. Antigens will be presented as panels. The figure will be split into different parts (e.g., Parts a, b, c, etc.) if all antigens are unable to be presented in a readable manner within one figure.

Figure 7: Mean Specific Activity for sIgA as measured by the Binding Antibody Multiplex Assay and Associated 95% Confidence Intervals by Antigen, Cohort, and Vaccination Group – Modified Intent-to-Treat Population

Implementation Note: This will be similar to Figure 3. Antigens will be presented as panels. The figure will be split into different parts (e.g., Parts a, b, c, etc.) if all antigens are unable to be presented in a readable manner within one figure.

Figure 8: Geometric Mean Hemagglutination Inhibition (HAI) Antibody Titers in Plasma Against A/Singapore/INFIMH-16-0019/2016 and Associated 95% Confidence Intervals by Cohort and Vaccination Group – Modified Intent-to-Treat Population

Implementation Note: This will be similar to Figure 3.

Figure 9: Geometric Mean Influenza Microneutralization (MN) Antibody Titers in Plasma Against A/Singapore/INFIMH-16-0019/2016 and Associated 95% Confidence Intervals by Cohort and Vaccination Group – Modified Intent-to-Treat Population

Implementation Note: This will be similar to Figure 3.

Figure 10: Geometric Mean Neuraminidase Inhibition (NAI) Titers in Plasma Against A/Singapore/INFIMH-16-0019/2016 and Associated 95% Confidence Intervals by Cohort and Vaccination Group – Modified Intent-to-Treat Population

Implementation Note: This will be similar to Figure 3.

Figure 11: Geometric Mean sIgA Titer Against A/Singapore/INFIMH-16-0019/2016 as Measured by the Enzyme Linked Immunosorbent Assays and Associated 95% Confidence Intervals by Cohort and Vaccination Group – Modified Intent-to-Treat Population

Implementation Note: This will be similar to Figure 3.

Figure 12: Mean Total sIgA Concentration Against A/Singapore/INFIMH-16-0019/2016 as Measured by the Enzyme Linked Immunosorbent Assays and Associated 95% Confidence Intervals by Cohort and Vaccination Group – Modified Intent-to-Treat Population

Implementation Note: This will be similar to Figure 3.

[figure not shown]
Figure 13: Mean Normalized sIgA Against A/Singapore/INFIMH-16-0019/2016 as Measured by the Enzyme Linked Immunosorbent Assays and Associated 95% Confidence Intervals by Cohort and Vaccination Group – Modified Intent-to-Treat Population

Implementation Note: This will be similar to Figure 3.

14.3.1.1 **Solicited Adverse Events**

Figure 14: Maximum Severity of Local Solicited Events Post Dose 1 by Symptom – Participants 9-17 Years Old – Safety Population

Implementation Note: This is an example figure. The y-axis label will be “Symptom” and each row on the y-axis will present all applicable local solicited events as well as a row for “Any Local Solicited Event”. Panels will be included for each analysis group (9-17 yrs, 10^9 TCID₅₀ Sing2016 M2SR, 1 Dose; 9-17 yrs, Placebo, 1 Dose)

Similar Figures:

Figure 15: Maximum Severity of Local Solicited Events Post Dose 1 by Symptom – Participants 2-8 Years Old – Safety Population

Implementation Note: This will be similar to Figure 14. Groups include: 2-8 yrs, 10^9 TCID₅₀ Sing2016 M2SR, 1 or 2 Doses; 2-8 yrs, 10^8 TCID₅₀ Sing2016 M2SR, 1 Dose; 2-8 yrs, Placebo, 1 or 2 Doses

Figure 16: Maximum Severity of Local Solicited Events Post Dose 1 by Symptom – All Participants – Safety Population

Implementation Note: This will be similar to Figure 14. Groups include: Vaccine Recipients, Placebo Recipients

Figure 17: Maximum Severity of Local Solicited Events Post Dose 2 by Symptom – Participants 2-8 Years Old – Safety Population

Implementation Note: This will be similar to Figure 14. Groups include: 2-8 yrs, 10^9 TCID₅₀ Sing2016 M2SR, 2 Doses; 2-8 yrs, Placebo, 2 Doses

Figure 18: Maximum Severity of Local Solicited Events Post Any Dose by Symptom, Participants 2-8 Years Old – Safety Population

Implementation Note: This will be similar to Figure 14. Groups include: 2-8 yrs, 10^9 TCID₅₀ Sing2016 M2SR, 2 Doses; 2-8 yrs, Placebo, 2 Doses

Figure 19: Maximum Severity of Systemic Solicited Events by Symptom – Participants 9-17 Years Old – Safety Population

Implementation Note: This will be similar to Figure 14. Groups include: 9-17 yrs, 10^9 TCID₅₀ Sing2016 M2SR, 1 Dose; 9-17 yrs, Placebo, 1 Dose

Figure 20: Maximum Severity of Systemic Solicited Events Post Dose 1 by Symptom – Participants 2-8 Years Old – Safety Population

Implementation Note: This will be similar to Figure 14. Groups include: 2-8 yrs, 10^9 TCID₅₀ Sing2016 M2SR, 1 or 2 Doses; 2-8 yrs, 10^8 TCID₅₀ Sing2016 M2SR, 1 Dose; 2-8 yrs, Placebo, 1 or 2 Doses

Figure 21: Maximum Severity of Systemic Solicited Events Post Dose 1 by Symptom – All Participants – Safety Population

Implementation Note: This will be similar to Figure 14. Groups include: Vaccine Recipients, Placebo Recipients

Figure 22: Maximum Severity of Systemic Solicited Events Post Dose 2 by Symptom – Participants 2-8 Years Old – Safety Population

Implementation Note: This will be similar to Figure 14. Groups include: 2-8 yrs, 10^9 TCID₅₀ Sing2016 M2SR, 2 Doses; 2-8 yrs, Placebo, 2 Doses

Figure 23: Maximum Severity of Systemic Solicited Events Post Any Dose by Symptom – Participants 2-8 Years Old – Safety Population

Implementation Note: This will be similar to Figure 14. Groups include: 2-8 yrs, 10^9 TCID₅₀ Sing2016 M2SR, 2 Doses; 2-8 yrs, Placebo, 2 Doses

Figure 24: Maximum Severity of Local Solicited Events by Days Post Dose 1 – Participants 9-17 Years Old – Safety Population

Implementation Note: This is an example figure. Panels will be included for each analysis group (9-17 yrs, 10^9 TCID₅₀ Sing2016 M2SR, 1 Dose; 9-17 yrs, Placebo, 1 Dose). “Day 8” should be labeled as “Day 8+”

[figure not shown]

Figure 25: Maximum Severity of Local Solicited Events by Days Post Dose 1 – Participants 2-8 Years Old – Safety Population

Implementation Note: This will be similar to Figure 24. Groups include: 2-8 yrs, 10^9 TCID₅₀ Sing2016 M2SR, 1 or 2 Doses; 2-8 yrs, 10^8 TCID₅₀ Sing2016 M2SR, 1 Dose; 2-8 yrs, Placebo, 1 or 2 Doses

Figure 26: Maximum Severity of Local Solicited Events by Days Post Dose 1 – All Participants – Safety Population

Implementation Note: This will be similar to Figure 24. Groups include: Vaccine Recipients, Placebo Recipients

Figure 27: Maximum Severity of Local Solicited Events by Days Post Dose 2 – Participants 2-8 Years Old – Safety Population

Implementation Note: This will be similar to Figure 24. Groups include: 2-8 yrs, 10^9 TCID₅₀ Sing2016 M2SR, 2 Doses; 2-8 yrs, Placebo, 2 Doses

Figure 28: Maximum Severity of Local Solicited Events by Days Post Dose Following Any Dose – Participants 2-8 Years Old – Safety Population

Implementation Note: This will be similar to Figure 24. Groups include: 2-8 yrs, 10^9 TCID₅₀ Sing2016 M2SR, 2 Doses; 2-8 yrs, Placebo, 2 Doses

Figure 29: Maximum Severity of Systemic Solicited Events by Days Post Dose – Participants 9-17 Years Old – Safety Population

Implementation Note This will be similar to Figure 24. Groups include: 9-17 yrs, 10^9 TCID₅₀ Sing2016 M2SR, 1 Dose; 9-17 yrs, Placebo, 1 Dose

Figure 30: Maximum Severity of Systemic Solicited Events by Days Post Dose 1 – Participants 2-8 Years Old – Safety Population

Implementation Note: This will be similar to Figure 24. Groups include: 2-8 yrs, 10^9 TCID₅₀ Sing2016 M2SR, 1 or 2 Doses; 2-8 yrs, 10^8 TCID₅₀ Sing2016 M2SR, 1 Dose; 2-8 yrs, Placebo, 1 or 2 Doses

Figure 31: Maximum Severity of Systemic Solicited Events by Days Post Dose 1 – All Participants – Safety Population

Implementation Note: This will be similar to Figure 24. Groups include: Vaccine Recipients, Placebo Recipients

Figure 32: Maximum Severity of Systemic Solicited Events by Days Post Dose 2 – Participants 2-8 Years Old – Safety Population

[figure not shown]
Implementation Note: This will be similar to Figure 24. Groups include: 2-8 yrs, 10^9 TCID₅₀ Sing2016 M2SR, 2 Doses; 2-8 yrs, Placebo, 2 Doses

Figure 33: Maximum Severity of Systemic Solicited Events by Days Post Dose Following Any Dose – Participants 2-8 Years Old – Safety Population

Implementation Note: This will be similar to Figure 24. Groups include: 2-8 yrs, 10^9 TCID₅₀ Sing2016 M2SR, 2 Doses; 2-8 yrs, Placebo, 2 Doses

